2.6.2 Statistical hypothesis, model, and method of analysis

No inferential statistical methods are planned. Descriptive statistics will be used to summarize data.

2.6.3 Handling of missing values/censoring/discontinuations

Missing data handling for HSS7, ISS7, and UAS7 score

Refer to Section 2.5.3.

Missing data handling for AAS7 score

The weekly score AAS7 will be derived by adding up the daily scores of the 7 days preceding the visit. The weekly score will then range from 0 to 105.

For each weekly score from AAS, if one or more of the daily scores are missing, then the following principles will be applied to handle the missing data:

- If a patient has at least 4 non-missing daily scores within the 7 days prior to the study visit, then the weekly score will be calculated as the sum of the available eDiary scores of that week, divided by the number of non-missing days multiplied by 7.
- If there are less than 4 non-missing daily scores within the prior 7 days, then the weekly score will be missing for that week.

Missing data handling for DLQI score

There was a very high success rate of accurate completion of the DLQI. However, if responses were incomplete, the following rules were applied:

1. If one question was left unanswered, then the missing value was imputed to a 0 score and the overall DLQI/CDLQI score was summed up in the usual way out of 30.
2. If two or more questions were left unanswered, then the questionnaire was not scored (left to missing).
3. If question no. 7 was answered 'yes', then it was scored to a value of '3'. If question no. 7 was answered 'not relevant' then the score was 0. If question was answered 'no' (not being preventing to work or study) but the skin was a problem for working or studying, then the scores per possible response were either 'a lot' (2) or 'a little' (1) or not at all (0).

Missing data imputation for UAS7=0, UAS7≤ 6, DLQI=0-1, and AAS7=0 response

In analyses of above mentioned secondary efficacy endpoints, missing values with respect to response variables based on UAS7 score, DLQI/CDLQI score will be imputed as described in Section 2.6.1.

Multiple imputation methods refer to Section 2.5.3.

2.7 Analysis of secondary efficacy objective(s)

No other secondary efficacy objectives were analyzed.

2.8 Safety analyses

For all safety analyses, the safety set (or subpopulations within SAF) will be used. All subjects enrolled into the extension study, regardless of which preceding studies they came from will be included in the safety analysis. All listings and tables will be presented by treatment group. All data will be included in the analysis regardless of rescue medication use.

All safety analyses to be performed in this study are described and summarized in **Table 2-10**.

Table 2-10 Overview of analyses on secondary [REDACTED]

Analysis Population and Analysis Period	Endpoints and Analysis
Secondary Objective: to assess the safety and tolerability of ligelizumab in all subjects	

Population: SAF Period: entire study
	
 • TEAE, TESAE, TEAESI (crude incidence), by study period • Related TEAE, TEAEs leading to discontinuation, death (crude incidence), by study period • Summary of vital signs, by visit, by study period • Summary of lab assessments, by visit, by study period

Population: Continuous long term treatment subpopulation Period: TRT1+TRT2
	
 • TEAE, TESAE, TEAESI (crude incidence), by study period • Related TEAE, TEAEs leading to discontinuation, death (crude incidence), by study period • Summary of vital signs, by visit, by study period • Summary of lab assessments, by visit, by study period

Population: Long term treatment subpopulation Period: TRT1A; TRT1B; TRT2; TRT1+TRT2
	
 • TEAE, TESAE, TEAESI (crude incidence and EAIR) • TEAEs leading to discontinuation (crude incidence and EAIR) • Summary of clinical notable lab abnormality (only TRT1+TRT2) • Summary of newly occurring or worsening vital signs (hypertension, hypotension, bradycardia, tachycardia; only TRT1+TRT2)

Population: Long term treatment with a rest subpopulation Period: TRT1A; TRT1B; TRT2
	
 • TEAE, TESAE (crude incidence and EAIR) • TEAEs leading to discontinuation (crude incidence and EAIR) • AESI of CCV and malignancy (crude incidence and EAIR; TRT1+OBS2+TRT2+FU) • Summary of clinical notable lab abnormality (only TRT1+OBS2+TRT2+FU) • Summary of newly occurring or worsening vital signs (hypertension, hypotension, bradycardia, tachycardia; only TRT1+OBS2+TRT2+FU)

Secondary Objective: to assess the safety and tolerability of ligelizumab 120 mg q4w 1mL pre-filled syringe (PFS)	

Population: PFS subpopulation (by treatment group + total) Period: week 12 onwards (TRT1B+TRT2)
	
• TEAE, TESAE, TEAESI (crude and exp.adjusted incidence)• Related TEAE, TEAEs leading to discontinuation, death (crude incidence), by study period• Summary of vital signs, by visit• Summary of lab assessments, by visit
Secondary Objective: to assess the safety and tolerability of ligelizumab 120 mg q4w in all subjects who self-administer	

Population: self-administer subpopulation (by treatment group + total) Period: during TRT1B+TRT2, after first dose of self-administer
	
• TEAE, TESAE, TEAESI (crude and exp.adjusted incidence)• Related TEAE, TEAEs leading to discontinuation, death(crude incidence), by study period• Summary of vital signs, by visit• Summary of lab assessments, by visit

2.8.1 Adverse events (AEs)

2.8.1.1 General information

All adverse events (AEs) reported will be coded using MedDRA and summarized by treatment group, primary System Organ Class (SOC) and Preferred Term (PT).

Summary tables and/or listings will be provided for non-treatment emergent AEs by study period on an as-needed basis.

Treatment emergent AEs will be summarized by actually received treatment, in relevant treatment periods (see **Table 2-10**).

Treatment emergent AEs (TEAE) are defined as:

- Events started after the first dose of study treatment (ligelizumab) in the extension study and within 16 weeks of last dose of study treatment
- Events present prior to the first dose of study treatment (ligelizumab) in the extension study but:
 - increased in severity based on preferred term (e.g. worsening of headache),
 - same PT but increased severity (e.g. from mild to moderate),
 - same PT but increase in seriousness (from non-serious AE to SAE; if already a SAE from medical significant to LT/fatal)

TEAEs which will be counted for a specific treatment period are those which are those with an onset after the start of the treatment period, or which were present prior to the start of the treatment period but get worsen (increased in severity based on preferred term, or same PT but increased severity, or same PT but increase in seriousness) after the start of the treatment period. Within a specific treatment period, a subject with multiple AEs within a primary system organ class is only counted once with the greatest severity at the system organ class level, where applicable, towards the total of the primary system organ class.

Overview tables for the numbers and percentage of subjects with TEAE will be provided for:

- Any event (AE of special interest, related AE, SAE)
- Maximum intensity of events.
- Events with outcome of death.
- Other significant AEs leading to treatment discontinuation

2.8.1.2 Crude and Exposure-Adjusted Incidence Rate

The crude incidence rate is defined as the percentage of subjects with a specific adverse event divided by the total number of subjects in each study group.

In a long-term follow-up of the patients, the crude incidence rate might not be a correct measure because it does not include the individual subject's total exposure time in the calculation. As described in **Table 2-10**, the exposure-adjusted incidence rate (EAIR) will be provided for the safety analysis in certain study periods in addition to the crude rate.

The EAIR is defined as the number of subjects with a specific event divided by the total exposure-time among the subjects in the study group. That is, the EAIR is calculated as:

$EAIR = n / \sum t_i$, where n is the number of subjects having the i^{th} type event, and t_i is a subject's exposure time until having an i^{th} type event. If a subject has multiple events of the i^{th} type, the t_i is the time of the first event of that type. For a subject having no event of the i^{th} type, the t_i is the last follow-up time for that subject. The total exposure time of all subjects in a treatment group is $\sum t_i$. The EAIR is interpreted as the number of events occurring in a population per unit time. The exact Poisson 95% confidence interval for the EAIR will be provided as well, where

an exact $100*(1-\alpha)\%$ confidence interval will be derived as follows (Garwood 1936, Sahai and Khurshid 1993):

- Lower confidence limit $L = \frac{0.5C_{\alpha/2,2n}}{\sum t_i}$ for $n>0$, 0 otherwise,
- Upper confidence limit $U = \frac{0.5C_{1-\alpha/2,2n+2}}{\sum t_i}$,

where $C_{\alpha,k}$ is the α th quantile of the Chi-square distribution with k degrees of freedom.

Whenever applicable, exposure adjusted incidence rates will be provided for the type as below:

1. TEAE and TESAE: Primary SOC level and preferred term level
2. Treatment emergent AE of special interest: up to SMQ level 5

When calculating EAIR for AESI of cardiovascular and cerebrovascular (CCV) and malignancy, the adverse event and exposure time both consider the entire study period after the first study treatment.

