12.8 Sample size calculation

12.8.1 Primary endpoint(s)

The total number of subjects enrolled will be determined by the drop-out rate prior to the Phase 3 extension study from studies CQGE031C2302, CQGE031C2303, CQGE031C2202 and CQGE031C1301.

Based on interim results from CQGE031C2201, it is assumed that the proportion of subjects achieving $UAS7 \leq 6$ at Week 12 is around 55% for ligelizumab 72 mg q4w. It is assumed that the well-controlled response for ligelizumab 120 mg q4w will be similar. The corresponding

95% confidence interval is listed based on different assumptions of number of subjects who will be enrolled for each treatment arm.

Table 12-1 95% confidence interval based on number of subjects enrolled from the core studies (CQGE031C2302/2303)

Number of subjects enrolled	Number of subjects for each treatment group	Drop out rate at Week 12	Assumed proportion of subjects achieving UAS7 ≤ 6 at Week 12	Corresponding 95% confidence interval
500	250	10%	55%	(48.6% - 61.6%)
900	450	10%	55%	(50.2% - 59.9%)
1200	600	10%	55%	(50.8% - 59.2%)

To evaluate the retreatment efficacy in the subgroup of subjects who achieved $UAS7 \leq 6$ at Week 12 after the retreatment on the same ligelizumab dose, the 95% confidence interval of the response rate will be provided for each treatment group. It is assumed that 50% of subjects enrolled into this extension study were well-controlled responders during the core studies for each ligelizumab treatment group. A 15% drop out rate is assumed for each treatment group before Week 12. The number of subjects required at the baseline of re-treatment for each treatment arm is listed in [Table 12-2](#) below, based on different assumptions of the retreatment response rates and the corresponding precision levels (width of the 95% confidence interval).

Table 12-2 Number of subjects required at the baseline of re-treatment for each treatment arm enrolled from the core studies (CQGE031C2302/2303)

Response rate after retreatment	Precision		
	10%	12%	15%
70%	191	135	85
80%	146	102	66
90%	83	59	38

[figure not shown]
13 Ethical considerations and administrative procedures

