2.1.1 General definitions

2.1.1.1 Study Treatment

Study treatment groups used for analysis are defined as below:

- ligelizumab 72 mg q4w liquid in vial – ligelizumab 120 mg q4w PFS
- ligelizumab 120 mg q4w liquid in vial – ligelizumab 120 mg q4w PFS

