2.13.2.8 Overview of unplanned interim analysis

Table 2-15 Overview of unplanned interim analysis

Population/ Analysis /Study Period	Endpoints

Analysis: Efficacy
 
Population:
 
SAF
 
Outside-of-clinic self-administration subpopulation
 
Self-administration subpopulation
 
In-clinic staff-administration subpopulation
 
Study period:
 
TRT1
	
 • Proportion of subjects with well-controlled urticaria (UAS7 ≤ 6) by visit • The proportion of subjects with completely controlled disease (UAS7 = 0) by visit • The proportion of subjects with ISS7 = 0 by visit • The proportion of subjects with HSS7 = 0 by visit • Absolute change from extension study baseline in the UAS7 and its components (ISS7 and HSS7) by visit 
█ [REDACTED]

Analysis: Safety
 
Population:
 
SAF
 
Outside-of-clinic self-administration subpopulation
 
Self-administration subpopulation
 
In-clinic staff-administration subpopulation
 
Study period:
 
Week 0—12 in TRT1
 
Week 12—24 in TRT1
 
Week 24 onwards up to interim data cut off
 
Entire study up to interim data cut off
	
The crude incidence and exposure adjusted incidence will be provided for:
 
 • TEAE • Study treatment related TEAE • TESAE • TEAESI • TEAEs leading to discontinuation 
Other:
 
 • Listing of TEAEs leading to drug interruption • Crude incidence of TEAE by severity • Listing of adjudicated AE

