
Analysis: Safety
 
Population: SAF
 
Period: TRT1A; TRT1B
	
 • TEAE, TESAE, TEAESI (crude incidence and EAIR) • TEAEs leading to discontinuation, death, (crude incidence and EAIR) • TEAE by severity (crude incidence) • Summary of vital signs, by visit • Summary of lab assessments, by visit

Entire treatment period (TRT1 + TRT2)
	

Analysis: Safety
 
Population:
 
1) Long term treatment subpopulation
 
Period: TRT1A; TRT1B; TRT2; TRT1+TRT2
	
 • TEAE, TESAE (crude incidence and EAIR), TEAESI (crude incidence and EAIR) • TEAEs leading to discontinuation (crude incidence and EAIR) • Summary of clinical notable lab abnormality (only TRT1+TRT2) • Summary of newly occurring or worsening vital signs (hypertension, hypotension, bradycardia, tachycardia; only TRT1+TRT2)

Analysis: Safety
 
Population:
 
1) Long term treatment with a rest subpopulation
 
Period: TRT1A; TRT1B; TRT2
	
 • TEAE, TESAE (crude incidence and EAIR) • TEAEs leading to discontinuation (crude incidence and EAIR) • AESI of CCV and malignancy (crude incidence and EAIR; only TRT1+OBS2+TRT2+FU) • Summary of clinical notable lab abnormality (only TRT1+OBS2+TRT2+FU)

	
 Summary of newly occurring or worsening vital signs (hypertension, hypotension, bradycardia, tachycardia; only TRT1+OBS2+TRT2+FU)
Entire study period (for the legal requirements of ClinicalTrials.gov and EudraCT)	
Analysis: Safety Population: SAF Period: Entire study	
 TEAE which are not serious adverse events with an incidence greater than 5% TESAE and SAE suspected to be related to study treatment

3 Sample size calculation

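### As written, the crude adverse-event rates for the Safety Set in Weeks 12–52 (TRT1B) are divided by everyone in the study group, including subjects who never entered that period

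*SAP*

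**What the plan says.** SAP 2.8.1.2 defines the crude incidence rate as the "percentage of subjects with a specific adverse event divided by the total number of subjects in each study group" (I read percentage as number). It gives no separate denominator for a study period. SAP 2.1.1.1 defines the analysis groups as complete sequences, for example "ligelizumab 72 mg q4w liquid in vial – ligelizumab 120 mg q4w PFS". The Safety Set in SAP 2.2 is anyone dosed at least once.

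The numerator is limited by period. SAP 2.8.1.1 counts, for a given treatment period, "those with an onset after the start of the treatment period", plus earlier events that worsen after it starts.

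The definition feeds these tables:

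- **Final analysis.** SAP 2.8.1.3 and Table 2-16 report the Safety Set for TRT1A and TRT1B: "TEAE, TESAE, TEAESI (crude incidence and EAIR"), plus events leading to discontinuation and deaths. TEAEs by severity are given as crude incidence only.
- **General safety plan.** SAP Table 2-10, Safety Set row: "TEAE, TESAE, TEAESI (crude incidence), by study period".
- **Unplanned interim.** SAP 2.13.2.5.2 adopts the 2.8.1.2 definition. Table 2-15 covers the Safety Set and three administration subpopulations for Weeks 0–12, Weeks 12–24 and Week 24 onwards: "The crude incidence and exposure adjusted incidence will be provided for" TEAEs and related categories.

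**The concern.** A subject who stops before Week 12 has no PFS dosing period in which to have an event, yet the rule keeps that subject in the TRT1B denominator. The printed percentage then mixes two things: how often events occur among people treated in TRT1B, and how many people got that far.

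Non-entrants are expected. Protocol 12.8.1 states: "A 15% drop out rate is assumed for each treatment group before Week 12". SAP 2.5.1.1 has an intercurrent event for treatment stopped before Week 12 because the study was terminated. The interim rules in SAP 2.13.2.3.3 provide for subjects who had not reached Week 24 at the cut.

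At stake are published safety percentages for the first PFS period. No efficacy conclusion depends on this.

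**Working it through.** The documents state no crude adverse-event rate or period denominator, so there is no planned figure to reproduce.

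**Inputs**

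- Denominator: all subjects in the study group (SAP 2.8.1.2).
- Group size for illustration: 600 per group, the largest case in Protocol Table 12-1.
- Share not entering TRT1B, d: 10% (Protocol Table 12-1) or 15% (Protocol 12.8.1, responder subgroup). I take drop-out before Week 12 to mean not entering TRT1B.
- Rate among entrants, r: not in the documents. I use 5%, 20% and 40% as assumptions.

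**Check that the plan treats drop-out as lost subjects.** The first interval in Protocol Table 12-1 follows from 250 × 0.90 = 225 subjects and 124 responders: a Wald 95% interval for 124/225 is 48.6% to 61.6%, as printed. The 10% is therefore a real reduction in the number of subjects in the plan's own arithmetic.

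**Formula.** If non-entrants contribute no TRT1B events,

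reported rate = r × N × (1 − d) / N = r × (1 − d),

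and the relative understatement is d.

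**TRT1B, Safety Set, N = 600**

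| r among entrants | d = 10% (540 enter) | d = 15% (510 enter) |
|---|---|---|
| 5% | 27/600 = 4.5% | 25.5/600 = 4.25% |
| 20% | 108/600 = 18% | 102/600 = 17% |
| 40% | 216/600 = 36% | 204/600 = 34% |

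Dividing by entrants instead returns r: 108/540 = 102/510 = 20%.

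**Interim, Week 24 onwards.** The documents do not give d. Under assumed values of 10%, 30% and 50%, a rate of 20% among entrants prints as 18%, 14% and 10%.

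**Which sets have d = 0**

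- PFS subpopulation from Week 12: membership needs a PFS dose (SAP 2.2.2).
- Long-term subpopulations, with or without a rest: membership requires having reached the second half of treatment.
- Interim outside-of-clinic group in Week 24 onwards: home dosing first occurs at Week 24 (Protocol 4.1, 6.7).

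**Which sets can have d > 0**

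- Safety Set in TRT1B, and at the interim in Weeks 12–24 and Week 24 onwards.
- Interim in-clinic staff-administered group in Week 24 onwards: all its PFS injections are given by site staff, with no requirement to have reached Week 24.
- Interim self-administration group in Week 24 onwards: it counts in-clinic self-injection, which starts at Week 12 (Protocol 6.7.2).

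**The case against.** The strongest reply is that the SAP never says what study group means within a period. SAP 2.8.1.1 summarises events by treatment actually received in the relevant periods, and Tables 2-7 and 2-14 set out treatment by period, so a programmer could use a period-specific N. The output shells, which might settle this, are in a separate document. This is fair as far as it goes, but the only rule on the page is "divided by the total number of subjects in each study group", and the groups in 2.1.1.1 are whole sequences. Followed literally, it gives the diluted figure.

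A second reply is that the consequence is limited. That largely stands. The exposure-adjusted rate sits beside each Safety Set TRT1B crude rate except TEAEs by severity, SAP 2.8.1.2 itself cautions about crude rates in long follow-up, and the disposition tables in SAP 2.3.4 report how many entered TRT1B. But a second measure does not correct a wrong percentage.

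Three stronger readings are tempting and not supported:

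- **That the PFS safety analysis is understated.** SAP 2.8.1.3 limits that analysis to PFS recipients. The PFS subpopulation is missing from SAP 2.14.1 and Table 2-16, although 2.14.5 refers back to 2.8.1. The Safety Set TRT1B table may therefore carry more weight for PFS than intended, but it is not the planned PFS analysis.
- **That at the interim only the in-clinic group is diluted, against home dosing.** The self-administration group and the Safety Set can be diluted too.
- **That dilution creates a spurious difference between the two dose sequences.** This needs different entry shares, and the documents give none. The interim pools all ligelizumab (SAP 2.13.2.2), so it has no dose columns.

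A last objection changes the remedy. TEAEs run to 16 weeks after the last dose, and first-half study weeks include the 12-week follow-up after early discontinuation (SAP 2.1.1.3.2). The SAP does not say to which period such events belong. If they fall in TRT1B by calendar time, changing the denominator alone would leave subjects in the numerator who are not in the denominator.

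**Conclusion.** The point holds for the Safety Set TRT1B tables in the final analysis. Read as written, their crude rates are multiplied by the share of subjects who enter TRT1B: 0.90 or 0.85 at the plan's assumed drop-out, a relative understatement of 10–15%. Early termination could make it larger, but the documents give no number. For Week 24 onwards at the interim, the Safety Set, self-administration and in-clinic groups can be diluted by an unknown amount.

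The size rests on three assumptions. Drop-out before Week 12 equals non-entry. The planning figures, set for core-study subjects, apply to a Safety Set that also includes subjects from CQGE031C2202 and CQGE031C1301. Non-entrants add no TRT1B events.

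This is worth correcting because a stated rule gives a wrong figure and the correction is cheap. TEAEs by severity matter most, since they have no exposure-adjusted rate beside them.

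**What to change.** In SAP 2.8.1.2, define the crude incidence for a period as the number of subjects who entered the period and had one or more TEAEs assigned to it, divided by the number who entered it. For treatment periods, entered should mean dosed at least once in that period. Print that N in the column header. State that TEAEs arising after discontinuation are assigned to the last period in which the subject was dosed, so that numerator and denominator cover the same people. Entire-study tables keep the whole group.

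SAP 2.8.1.3 says that the interim self-administration safety analyses have been done and will not be repeated. For those, confirm which N was used and add a footnote.

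The cost is a short addition to the SAP and changes to the denominator and period flag in the table programs. Entry to TRT1B is already counted for the disposition tables. Some printed percentages become slightly less favourable.

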2.8.1.3 AE summaries for Secondary Safety Endpoints

For safety and tolerability of ligelizumab for all subjects during the study, summaries will be provided by study period. For TRT1A and TRT1B, summaries of TEAE, treatment emergent SAE (TESAE), treatment emergent AESI (TEAESI), TEAEs leading to discontinuation, TEAEs leading to death, and TEAE by severity will be provided for SAF.

For the long term treatment subpopulation, TEAE, TESAE, TEAESI, and TEAEs leading to discontinuation will be summarized for TRT1A, TRT1B, TRT2 and TRT1+TRT2.

For the long term treatment with a rest subpopulation, TEAE, TESAE, TEAEs leading to discontinuation, AESI of CCV and malignancy will be summarized for TRT1A, TRT1B, and TRT2.

In addition, a summary table of TEAE during entire treatment period was planned to be provided for the continuous long term treatment subpopulation. However, this analysis will not be conducted in the final analysis due to study early termination due to study early termination.

To investigate the safety and tolerability of ligelizumab 120 mg PFS, summaries of TEAEs, TESAEs, and TEAESIs will be provided to include the AEs after the first dose of PFS use. Only the subjects who receive at least one dose of ligelizumab 120 mg PFS use will be included in this analysis.

To investigate the safety and tolerability of ligelizumab 120 mg in all subjects who will be self-administered, summaries on TEAEs, TESAEs, and TEAESIs will be provided to include the information after the first dose using “out of clinic” self-administration. Subjects who move from self-administration back to in-clinic administration during the study, will be included in this analysis if majority (>50%) of drug use is based on “out of clinic” self-administration.

The safety and tolerability of ligelizumab 120 mg self-administration with PFS has been evaluated at the interim analysis. Those analyses will not be re-conducted in the final analysis.

